12 REGULATORY AND ETHICAL OBLIGATION

12.1 APPLICABLE REGULATORY REQUIREMENTS

The study will be conducted in accordance with International Council for Harmonisation (ICH) and Good Clinical Practice (GCP) guidelines and all applicable national regulations.

The Sponsor will obtain the required approval from each national regulatory authority to conduct the study. During the conduct of the study, an annual safety report will be compiled by the Sponsor for submission to those regulatory authorities and IRBs/ECs that require it. Any additional national reporting requirements as specified by the applicable regulations, regulatory authorities, or IRB/EC will also be fulfilled during the conduct of the study.

12.2 INFORMED CONSENT REQUIREMENTS

Before a subject is enrolled in the study, the Investigator or his/her designees must explain the purpose and nature of the study, including potential benefits and risks and all study procedures to the subject. The subject must sign and date an IRB/EC-approved ICF prior to the conduct of any study-related activities. A copy of the signed consent form will be given to the subject and the original will be retained in the study site's records.

12.3 INDEPENDENT ETHICS COMMITTEE/INSTITUTIONAL REVIEW BOARD

Prior to study initiation at each site, the Investigator will obtain approval for the study from an appropriate IRB/EC and provide the Sponsor with a copy of the approval letter. The IRB/EC must also review and approve the study site's ICF and any other written information provided to the subject prior to enrollment, as well as any advertising materials used for subject recruitment. Copies of the ICF and advertising materials must be forwarded to the Sponsor for review before submission to the IRB/EC prior to the start of the study.

If, during the study, it is necessary to amend either the protocol or the ICF, the Investigator is responsible for obtaining IRB/EC approval of these amended documents prior to implementation. Copies of the IRB/EC correspondence and approval letters must be sent to the Sponsor.

During the conduct of the study, an annual progress report will be compiled by the Sponsor for submission to those IRBs/ECs that require it.

A written summary of the study will be provided by the Investigator to the IRB/EC following study completion or termination according to the IRB/EC's standard procedures. Additional updates will also be provided in accordance with the IRB/EC's standard procedures.

12.4 PRESTUDY DOCUMENTATION REQUIREMENTS

Before the commencement of the clinical study, at a minimum, the following documents will be provided to the site: Investigator's Brochure, Protocol, ICF, Subject Dosing Diary, the Tyvaso Inhalation System IFU, Clinical Trial Agreement, Budget Agreement, and eCRF.

At a minimum, the site will be required to provide the following documents to United Therapeutics Corporation or designee prior to study start: Signature page of the protocol, Form FDA 1572, Financial Disclosure Form, IRB/EC Composition and Roster, IRB/EC protocol and informed consent approval letters, and Curriculum Vitae of study staff listed on the Form FDA 1572.

12.5 SUBJECT CONFIDENTIALITY

Every effort will be made to keep medical information confidential. United Therapeutics Corporation, the FDA or other regulatory bodies, and the IRB/EC governing this study may inspect the medical records of any subject involved in this study. The Investigator may release the subject's medical records to employees or agents of the Sponsor, the IRB/EC or the FDA or appropriate local regulatory agencies for purposes of checking the accuracy of the data. A number will be assigned to all subjects and any report published will not identify the subject's name.

13 ADMINISTRATIVE AND LEGAL OBLIGATIONS

13.1 PROTOCOL AMENDMENTS AND STUDY TERMINATION

Protocol amendments that could potentially adversely affect the safety of participating subjects or that alter the scope of the investigation, the scientific quality of the study, the experimental design, dosages, duration of therapy, assessment variables, the number of subjects treated, or subject selection criteria may be made only after consultation between United Therapeutics Corporation or its designee and the Investigator.

All protocol amendments must be submitted to and approved by the appropriate regulatory authorities and IRB/EC prior to implementation.

A report documenting study termination must also be submitted to and acknowledged by the appropriate IRB/EC for each study site.

At the end of the study, where applicable, a final report will be provided to the local regulatory agencies.

13.2 STUDY DOCUMENTATION AND STORAGE

In accordance with federal/national regulations, ICH, and GCP guidelines, the Investigator must retain study records for at least 2 years after the last approval of a marketing application in an ICH region and until there are no pending or contemplated marketing applications in an ICH region or at least 2 years have elapsed since the formal discontinuation of clinical development of the investigational product. The Investigator must notify United Therapeutics Corporation before any disposal or change in location of study records.

13.3 STUDY MONITORING AND DATA COLLECTION

In accordance with federal/national regulations, ICH, and GCP guidelines, monitors for United Therapeutics Corporation or its designee will periodically contact the site and conduct on-site visits. During these visits, the monitor will at a minimum: confirm ethical treatment of subjects, assess study progress, review data collected, conduct source document verification, verify drug accountability periodically, and identify any issues requiring resolution.

The Investigator agrees to allow the monitor direct access to all relevant documents and to allocate his/her time and his/her staff to the monitor to discuss any findings or any relevant issues.

15 APPENDICES

15.1 PROCEDURE FOR 6-MINUTE WALK TEST

General Procedures

The 6MWT should be administered by the same tester at each study site throughout the study, whenever possible. The administration of the test and specifications of the testing area should be generally consistent with the American Thoracic Society guidelines^{1,2} and the usual practice of the investigative site. Subjects receiving supplemental oxygen during the Baseline 6MWT must continue to receive the same flow rate at all subsequent 6MWT assessments.

The area used for the 6MWT should be pre-measured at approximately 30 meters in length and at least 2 to 3 meters in width. There must be no turns or significant curves to the 6MWT area. The length should be marked with gradations to ensure the accurate measurement of the distance walked. The area should be well ventilated. The tester may be at the starting end of the corridor or at the midpoint of the corridor with a stop-watch. Intermittent rest periods are allowed if the subject can no longer continue. If the subject needs to rest briefly, he/she may stand or sit and then begin again when he/she is sufficiently rested but the clock will continue to run. At the end of 6 minutes, the tester will call "stop where you are" while simultaneously stopping the watch and then measure the distance walked.

Instructions to the Subject

Subjects will be instructed that the preceding meal should be light. Subjects should be told to wear comfortable clothing and sneakers or comfortable walking shoes. The person administering the test will use the following **exact** dialogue with the subject:

"The purpose of this test is to find out how far you can walk in 6 minutes. You will start from this point and follow the hallway to the marker (eg, chair) at the end, turn around and walk back. When you arrive back at the starting point you will go back

¹ ATS Statement: Guidelines for the Six-Minute Walk Test. Am J Respir Crit Care Med 2002; 166: 111 117.

² Holland, A. E., M. A. Spruit, T. Troosters, M. A. Puhan, V. Pepin, D. Saey, M. C. McCormack, B. W. Carlin, F. C. Sciurba, F. Pitta, J. Wanger, N. MacIntyre, D. A. Kaminsky, B. H. Culver, S. M. Revill, N. A. Hernandes, V. Andrianopoulos, C. A. Camillo, K. E. Mitchell, A. L. Lee, C. J. Hill and S. J. Singh (2014). "An official European Respiratory Society/American Thoracic Society technical standard: field walking tests in chronic respiratory disease." Eur Respir J 44(6): 1428-1446.

and forth again. You will go back and forth as many times as you can in the 6-minute period. You may stop and rest if you need to. Just remain where you are until you can go on again. However, the most important thing about the test is that you cover as much ground as you possibly can during the 6-minutes. I will tell you the time, and I will let you know when the 6 minutes are up. When I say 'STOP,' please stand right where you are."

After these instructions are given to the subject, the person administering the test will then ask:

"Do you have any questions about the test?"

The person administering the test will then start the test by saying the following to the subject:

```
"Are you ready?"
```

"Start when I say 'GO.""

The person administering the test will tell the subject the time at each minute by saying:

```
"You have 5 minutes to go."
```

At 6 minutes, the person administering the test will tell the subject:

```
"Stop where you are."
```

No other instruction or encouragement will be given during the test. Eye contact with the subject should be avoided during the test.

[&]quot;You have 4 minutes to go."

[&]quot;You have 3 minutes to go."

[&]quot;You have 2 minutes to go."

[&]quot;You have 1 minute to go."

15.2 GUIDELINES AND DEFINITIONS FOR RECORDING ADVERSE EVENTS

The Investigator or a designated member of his/her staff will probe each subject for any AEs that may have occurred. The Investigator should always ask the same question when conducting the verbal probe in order to ensure uniformity between subjects. The Investigator should ask:

"How are you doing (feeling)?"

Based on the subject's response to this question, the Investigator should ask additional questions relevant to the specific complaint such as:

"How severe is/was the symptom?"

"How often did the symptom occur?"

"How long did the symptom last?"

It is the Investigator's responsibility to review the results of all diagnostic and laboratory tests as they become available and ascertain if there is a clinically significant change from Baseline. If the results are determined to be a clinically significant change from Baseline, this should be reported as an AE. The Investigator may repeat the diagnostic procedure or laboratory test or request additional tests to verify the results of the original tests. When possible, a diagnosis associated with the abnormality should be used as the reported AE.

Using provided definitions, the Investigator will then:

(1) rate the intensity and seriousness of the AE, (2) estimate the causality of the AE to study drug, and (3) note actions taken to counteract the AE.

Definitions of Intensity, Seriousness, Causality, Action Taken, and Outcome

INTENSITY

An assessment of the relative intensity (severity) of an AE is based on the Investigator's clinical judgment. The maximum intensity encountered during the evaluation period should be checked. The assessment of intensity should be independent of the assessment of the seriousness of the AE.

SERIOUSNESS

A serious AE is one that represents an actual or potential significant hazard. This includes, but is not limited to, an event that is fatal, life-threatening, permanently or severely disabling, requires or prolongs inpatient hospitalization*, is a congenital abnormality (offspring of subject) or is medically significant (important medical events that may not result in death, be life-threatening, or require hospitalization may be considered an SAE when, based upon appropriate medical judgment, they may jeopardize the subject and may require medical or surgical intervention to prevent 1 of the outcomes listed in this definition).

*Hospitalizations that would not be considered SAEs include those for:

- Routine treatment or monitoring of the study indication not associated with any deterioration in condition (eg, hospitalization for a routine RHC).
- Treatment which was elective or pre-planned, for a pre-existing condition not associated with any deterioration in condition (eg, pre-planned operation which does not lead to further complications etc).
- Treatment of an emergency, in an outpatient setting for an event not fulfilling any of the definitions of serious as given above and not resulting in hospital admission.

CAUSALITY

An estimate of causality between a specified AE and the study drug is made by the Investigator. Several factors should be considered when determining causality. These factors include temporal relationship and response to withdrawal or reintroduction of the study drug.

Definitions of the causality categories are as follows:

- NOT RELATED There is not a temporal relationship to study drug administration (too early, or late, or study drug not taken), or there is a reasonable causal relationship between another drug, or concurrent disease and the SAE, or any of the following:
 - An event that precedes the first administration of study drug
 - o An event for which the cause is clearly related to an external event
 - o Temporal relationship to study drug is atypical
 - Is readily explained by an intercurrent illness AND has an expected level of severity, duration, and resolution
 - o An alternative explanation (concomitant drug, intercurrent illness) is likely
- POSSIBLE There is a reasonable causal relationship between the study drug and the SAE. Dechallenge information is lacking or unclear, study drug administration was not modified in response to the SAE, or any of the following:

- Has a reasonable temporal relationship to study drug
- o The event has a plausible biological link to the activity of the study drug
- Is unlikely to be related to an intercurrent illness or has an unexpected degree of severity, duration or complication
- PROBABLE There is a reasonable causal relationship between the study drug and the SAE. The event responds to dechallenge - the event resolves or improves with modification of study drug administration. Rechallenge (the original study drug was restarted) is not required, or any of the following:
 - Has a reasonable temporal relationship to study drug
 - o The event has a plausible biologic link to the activity of the study drug
 - Not readily explained by an intercurrent illness
 - Not readily explained by external event
 - Improves on discontinuation of study drug
 - o If study drug has been discontinued, may recur or reintroduction of study drug

ACTION TAKEN

STUDY DRUG DOSE MODIFICATION*

- Dose Not Changed The dose or regimen of the study drug was not changed.
- Dose Increased The dose or regimen of study drug was increased
- Dose Decreased The dose or regimen of study drug was decreased
- Drug Interrupted Administration of the study drug was stopped temporarily
- Drug Withdrawn Administration of the study drug was stopped permanently and not restarted
- Unknown Changes to the administration of the study drug cannot be determined
- Not Applicable

*NOTE: Only the last study drug action should be recorded in the eCRF. For example, if the study drug is withdrawn and then the decision is made to restart, the dose modification of "Drug interrupted" should be reported on the SAE form.

OUTCOME

- Fatal The study subject died.
- Not Recovered/Not Resolved The AE was ongoing at the time of death or at the time the subject was lost to follow up.
- Recovered/Resolved The AE resolved.
- Recovered/Resolved with Sequelae The AE is considered resolved however there is
 residual sequelae. Some events do not return to baseline, such as metastasis or
 progression of disease; however, once these events are determined by the Investigator
 to be stable or chronic, the Investigator may consider the event to be resolved or
 resolved with sequelae.

- Recovering/Resolving The AE is improving but is not yet completely recovered/resolved.
- Unknown The outcome of the AE cannot be determined.

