6 DRUGS AND DOSING (OR TREATMENT PROCEDURES)

6.1 DRUG DOSAGE, ADMINISTRATION, AND SCHEDULE

Treprostinil for inhalation solution (0.6 mg/mL) is delivered via an ultrasonic nebulizer which emits a dose of approximately 6 mcg per breath. Placebo will be provided as an identical solution that will be inhaled using the same ultrasonic nebulizer. All subjects will receive study drug (inhaled treprostinil or placebo) using the commercially available TD-100 ultrasonic nebulizer (Tyvaso Inhalation System®). Subjects will be trained on inhalation of study drug using the nebulizer device. Detailed instructions for the use of these devices will be provided to all study subjects. In addition, all subjects will receive a copy of the commercially available Tyvaso Inhalation System Instructions for Use (IFU) for the TD-100 ultrasonic nebulizer.

Once informed consent has been signed, all entry criteria have been met, and the randomized treatment assignment confirmed, the first dose of study drug (3 breaths; 18 mcg) will be inhaled in the clinic, followed by at least a 1 hour observation period (defined as Day 1). Study drug doses should be maximized throughout the study, dose escalations (additional 1 breath 4 times daily) can occur up to every 3 days with a target dosing regimen of 9 breaths (54 mcg) 4 times daily and a maximum dose of 12 breaths (72 mcg) 4 times daily within 4 weeks of beginning the treatment, as clinically tolerated. Table 6-1 provides a guideline for the recommended dose escalations.

Table 6-1 Recommended Inhaled Treprostinil Dose Escalation Table

Study Day ^a	Single Dose	Total Daily Dose					
	Titrating to maximum dose of 12 breaths						
1-3	3 breaths QID (18 mcg)	72 mcg					
4-6	4 breaths QID (24 mcg)	96 mcg					
7-9	5 breaths QID (30 mcg)	120 mcg					
10-12	6 breaths QID (36 mcg)	144 mcg					
13-15	7 breaths QID (42 mcg)	168 mcg					
16-18	8 breaths QID (48 mcg)	192 mcg					
19-21	9 breaths QID (54 mcg)	216 mcg					
22-24	10 breaths QID (60 mcg)	240 mcg					
25-27	11 breaths QID (66 mcg)	264 mcg					
28 (and beyond)	12 breaths QID (72 mcg)	288 mcg					

Abbreviations: QID, 4 times daily; mcg,: micrograms

a Study day refers to the days on study drug with Day 1 referring to the first dose of study drug.

The dosing schedule is recommended as a guide only. The Investigator may determine the appropriate dosing schedule on an individual subject basis, considering tolerability and functional improvement.

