If subjects are unable to tolerate the initial 3 breaths, they may decrease their next dose to 1 or 2 breaths of study drug (as determined by the Investigator) 4 times a day during waking hours. The subject will then gradually increase their dose to reach a minimum of 3 breaths, and titrate to a target dose of 9 breaths and a maximum dose of 12 breaths 4 times a day during waking hours, as clinically tolerated.

Dose changes should be conducted under appropriate medical supervision in consultation with the study site. Telephone calls/emails between the site and subject should occur prior to each dose adjustment or at least weekly to monitor for AEs, clinical worsening events, and make decisions about dose titration.

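### Keeping only the last study drug action for each adverse event can lose the link between a temporary dose reduction or interruption and the event that caused it

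*Protocol*

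**What the plan says.** Protocol Appendix 15.2 asks the investigator, for each AE, to "note actions taken to counteract the AE". The list of permitted codes includes "Dose Increased The dose or regimen of study drug was increased" and "Drug Withdrawn Administration of the study drug was stopped permanently and not restarted", alongside codes for no change, decrease, interruption, unknown and not applicable. A note under the list sets the recording rule: "Only the last study drug action should be recorded in the eCRF". An example follows: "if the study drug is withdrawn and then the decision is made to restart, the dose modification of 'Drug interrupted' should be reported". The rule names the eCRF, whereas the example names the SAE form.

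For intensity, the same appendix uses a worst-case rule: "The maximum intensity encountered during the evaluation period should be checked".

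On dosing, Protocol Section 6.1 says "Study drug doses should be maximized throughout the study" and allows a step of one breath four times daily as often as every 3 days. For subjects who cannot tolerate the first 3 breaths, it says "they may decrease their next dose to 1 or 2 breaths of study drug", and then describes a gradual increase again.

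SAP Section 12.1 lists each dose change with its dose and date. SAP Section 12.2 lists every AE detail held on the eCRF and tabulates AEs leading to discontinuation of study drug (Table 14.3.1.8). No table is planned for AEs leading to a decrease or an interruption.

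**The concern.** The purpose of the field and the rule for filling it differ whenever the dose changes again after the counteracting step. In a trial that titrates upward throughout, that sequence is foreseeable: the dose is cut because of cough or headache, the event eases, and titration resumes. The last study drug action is then an increase.

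What is at stake is AE-level attribution. For a titrated inhaled drug, a basic tolerability question is which events forced subjects to step back temporarily. If the action code shows only the later increase, the AE listing cannot answer it, and the link may not be recoverable from the database. A code that describes a step taken for a different reason could also place an AE among those leading to discontinuation.

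**Working it through.** The plan states no figure on this point, so the check sets the passages side by side.

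**Step 1: apply the rule to each dosing history.** The literal column takes the last study drug action for any reason while the AE record is open. The purpose column takes the action made to counteract the AE.

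| Dosing history while the AE is open | Literal last action | Action for the AE | Covered by the example? |
|---|---|---|---|
| Decreased for the AE, no later change | Decreased | Decreased | Not needed |
| Decreased for the AE, then re-titrated | Increased | Decreased | No |
| Stopped, then restarted only | Interrupted (by the example) | Interrupted | Yes |
| Interrupted for the AE, restarted, then titrated further | Increased | Interrupted | No |
| Interrupted for the AE, later stopped permanently for another reason | Withdrawn | Interrupted | No |
| Stopped permanently because of the AE | Withdrawn | Withdrawn | Not needed |

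The two columns disagree in three of the six histories, and the example settles none of those three.

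**Step 2: can the re-titration happen while the record is still open?** At the fastest pace in Section 6.1 (one breath per 3 days), a decrease of k breaths can be regained in 3 × k days:

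- k = 1: 3 × 1 = 3 days.
- k = 2: 3 × 2 = 6 days. This is also the shortest path from 1 breath back to 3 after first-dose intolerance, if that general pace applies there.

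Protocol Sections 3.3.2.7 and 9.3 follow AEs to resolution, until no longer clinically significant, or for at least 30 days past the final visit. Section 9.3 also has eCRF pages updated as information arrives. Overlap is therefore plausible. Section 1.2.3 reports cough in 54% and headache in 41% of the active arm of the earlier placebo-controlled trial in PAH. Events that might prompt a dose change are thus not rare, although those figures are not rates of dose reduction.

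**Step 3: does another planned item hold the link?**

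- Protocol Section 9.2 names onset and cessation, intensity, seriousness, relationship and outcome. None says that the AE led to a decrease.
- SAP Section 12.1 names dose and date for each change, but no reason. Its compliance measure counts days with more than 0 breaths, so a decrease does not show there.
- The causality definitions in Appendix 15.2 use response to a dose modification to separate *Probable* from *Possible*. A *Probable* rating on that ground implies a modification but does not record which one. Beside *Dose Increased* it would look inconsistent.

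**Step 4: which planned outputs are exposed?** The AE listings print the code. Table 14.3.1.8 might be affected by the fifth history, but the SAP does not say which field selects AEs for that table.

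**Step 5: frequency.** The documents give no rate of AE-driven decreases, of re-titration after them, or of how sites read the note. The number affected cannot be computed.

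**The case against.** The strongest reply is that Appendix 15.2 defines the field as actions against the AE. Routine titration after an event settles does not counteract it, so a careful site would still code *Dose Decreased*. The example supports this. The code list has no restart code and reserves *Drug Withdrawn* for a permanent stop, so the last action may mean the final status of the drug for that event. This reading is available, but the note does not limit the last action to actions for that AE. *Dose Increased* is a permitted code, so two sites could code the same history differently.

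Other parts of the reply stand and limit the point. A reader might infer any of the following, and the documents do not support them:

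- **That the drug's intolerability is under-recorded as a whole.** The AE, its maximum intensity, its causality and permanent withdrawal are recorded, dose changes are listed with dates, and AEs are tabulated by dose at onset (Table 14.3.1.10).
- **That every interruption is overwritten.** The example keeps an interruption followed only by a restart.
- **That a planned tolerability table would be wrong.** No table of AEs leading to decrease or interruption is planned, and Protocol Section 10.3.4 plans no inferential analysis of AEs. SAP Section 9.1 lists the primary reason for stopping study drug, so a miscoded withdrawal could be cross-checked.
- **That the DMC would be misled, or that the effect falls mainly on the active arm.** The interim safety outputs are in a charter and a separate plan that are not in these documents. The titration rules apply to both arms.
- **That the size is known.** Suppose 10% to 30% of about 314 / 2 = 157 active subjects had an AE-driven reduction and 50% to 80% of them were re-escalated. Then 157 × 0.10 × 0.50 ≈ 8 to 157 × 0.30 × 0.80 ≈ 38 subjects would be involved. All four rates are assumptions with no source in the documents. The result also assumes that every site follows the literal reading and that no interruption is saved by the example. It is not evidence of size.

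**Conclusion.** The point holds as a limited data-recording defect. The note keeps one action per AE and selects it by order in time, while the field is meant to show the response to the AE. In a protocol that expects continued up-titration, the two can diverge in the three histories identified above. The consequence is lost or wrong attribution of a temporary dose change to its AE in the listings, and possibly a misplaced AE in Table 14.3.1.8.

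This rests on two assumptions: that at least some sites follow the note literally, and that the eCRF, which is not in the documents, has no separate item giving the reason for a dose change. No sample size, power, alpha or efficacy result depends on the point. It is worth correcting because the correction is cheap and the link may not be recoverable later.

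**What to change.** Replace the note in Appendix 15.2 with:

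> Record the most restrictive study drug action taken because of this AE, in the order Withdrawn, Interrupted, Decreased, Increased, Not Changed (Unknown or Not Applicable only if none of these applies). Later re-titration, or an action taken for another reason, does not replace it. A drug stopped and then restarted is recorded as Interrupted.

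Apply the same rule to the eCRF and the SAE form. It serves the stated purpose of the field, parallels the maximum rule for intensity, and gives the same answer as the note's own example. It concerns recording only and leaves the dosing and titration rules as they are.

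The cost is a short text change and a small update to the eCRF guidance; the field already exists. One visible effect is that more AEs will show a decrease or an interruption.
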